8.9.1.1 Screening Visit (Arm 3 only)

The following procedures will be performed and documented by the investigator or delegate:

- Demographics.
- Review inclusion and exclusion criteria.
- Social and physical activity.
- Relevant medical and treatment history.
- Physical examination.
- Vital signs.
- Body weight and height.
- Obtain blood samples for biochemistry and hematology.
- Obtain blood samples for:
 - Inhibitors against FIX.
 - Antibodies against rIX-FP.
 - Antibodies against CHO cell-derived proteins.
- Obtain blood sample for measurement of plasma FIX.
- Prior and concomitant therapy.
- Start monitoring of AEs.

8.9.1.2 Screening Visit (Arm 4 only)

The following procedures will be performed and documented by the investigator or delegate:

- Demographics.
- Review inclusion and exclusion criteria.
- Relevant medical history.
- Family history of inhibitor against FIX.

-
- Physical examination.
 - Vital signs.
 - Body weight and height.
 - Obtain blood samples for biochemistry and hematology, if feasible, unless results within 6 months are available in the subject's medical records.
 - Obtain blood sample for measurement of plasma FIX (LL), unless data is available in the subject's medical records.
 - Obtain blood samples for:
 - Inhibitors against FIX.
 - Antibodies against rIX-FP.
 - Antibodies against CHO cell-derived proteins.
 - Prior and concomitant therapy.
 - Start monitoring of AEs.
 - If a subject experiences a life-threatening bleeding episode (including bleeding in the central nervous system, gastrointestinal tract, neck/throat, or severe trauma-induced bleeding) or requires a major surgical procedure prior to the first administration of rIX-FP, the subject will not be enrolled into the study and will be counted as a screen failure.

8.9.1.3 Day 1 Visit (Arms 1 and 2 only)

The following information will be transferred from the end of study visit or earlier visit (where relevant) of the lead-in study:

- Information on demographics.
- Lead-in study data (rIX-FP EDs, age cohort in lead-in study [CSL654_3002 study only], arm in lead-in study [CSL654_3001 study only], prior therapies including treatment regimen at the end of the lead-in study).
- Social and physical activity.
- Physical examination.
- Vital signs.
- Body weight and height.

- Results from biochemistry and hematology assessments.
- Results for inhibitors against FIX, antibodies against rIX-FP, antibodies against CHO cell-derived proteins.
- Results for plasma FIX activity (CSL654_3001 subjects only).
- Concomitant therapy.
- Ongoing AEs.

The following procedures will be conducted at the Day 1 visit:

- Review inclusion and exclusion criteria.
- Record relevant medical history (genotype and joint score including scoring system and date of assessment).
- Obtain blood sample for measurement of plasma FIX activity (central laboratory) for subjects from the CSL654_3002 study.
- Start monitoring of AEs.
- Any new concomitant therapy (ie, not reported at the end of study visit of the lead-in study).
- Record the dose regimen (dose and treatment interval) and administration information in the eCRF, if the subject is administered the first injection of rIX-FP during the visit.
- Dispense eDiary.
- If considered necessary, reinstruct subject on injection technique, dosing regimen, and use of eDiary.
- Schedule next visit.

8.9.2 Day 1 Visit (Arms 3 and 4)

8.9.2.1 Day 1 (Arm 3 only, which excludes any subjects from France)

After completion of the surgery substudy, subjects must complete the Day 1 visit if they choose to remain in the study. This Day 1 visit will occur on the same day as the End of Surgery

Substudy visit. At this visit, the following procedures will be performed by the investigator or delegate:

- If necessary, reinstruct subject on injection technique.
- Body weight.
- Assign and instruct subject on dosing regimen.
- Record AEs and concomitant therapies.
- After the Day 1 visit, subjects in Arm 3 should complete the study according to [Table A - Schedule of Assessments: Treatment Period](#).

8.9.2.2 Day 1 visit (Arm 4 only)

The Day 1 visit may occur on the same day as the Screening visit, if all inclusion criteria are met.

The following procedures will be conducted at the Day 1 visit PRIOR to the administration of rIX-FP:

- Review inclusion and exclusion criteria to confirm eligibility for the study.
- Physical examination.
- Vital signs.
- Body weight and height.
- Collect blood samples prior to first dose of rIX-FP (if not collected at Screening):
 - Biochemistry and hematology (LL), unless results within 6 months are available in the subject's medical records.
 - Plasma FIX level (CL).
 - Inhibitors against FIX (CL).
 - Antibodies against rIX-FP and CHO cell-derived proteins (CL).
- Prior and concomitant therapy.
- Administer the first dose of rIX-FP.

The following procedures will be conducted at the Day 1 visit FOLLOWING the administration of rIX-FP:

- Monitor subject for at least 3 hours under medical supervision.

- Record the dose, administration information and reason for the dose in the eCRF.
- If the first dose is for PK assessment, sample for FIX activity will be collected 30 minutes post administration.
- Record AEs and concomitant therapy.

8.9.3 Other Visits during the Treatment Period (Arm 1, 2 and 3)

8.9.3.1 Month 3 Visit and Month 9 Visit

The following procedures will be performed and documented by the investigator or delegate:

- Body weight (omitted if visit conducted via telephone).
- Review subject eDiary.
- Assess treatment efficacy for major bleeding episodes, if applicable.
- Record AEs and concomitant therapies.
- If considered necessary, reinstruct subject on injection technique, dosing regimen, and use of eDiary.
- Schedule next visit.

For subjects from lead-in Study CSL654_3001 Arm 1, the visit at month 3 may be conducted via telephone, if the investigator deems that there is no safety risk to the subject.

For all Arm 2 and 3 subjects, the visit at month 9 may be conducted via telephone, if the investigator deems that there is no safety risk to the subject.

The month 3 visit may be omitted for subjects in Arm 2 who have attended a follow-up after visit in the previous 3 months to transition from a 7-day rIX-FP treatment interval to a 14-day rIX-FP treatment interval.

8.9.3.2 Month 6 Visit

The following procedures will be performed and documented by the investigator or delegate:

- Record social and physical activity.
- Body weight.

[figure not shown]
-
- Obtain blood samples for:
 - Inhibitors against FIX.
 - Plasma FIX activity) (central and local laboratory).
 - Review subject eDiary.
 - Assess treatment efficacy for major bleeding episodes, if applicable.
 - Review treatment regimen (ie, dose and / or treatment interval) and modify, if necessary. Record any changes in treatment regimen in the eCRF.
 - Record AEs and concomitant therapies.
 - If considered necessary, reinstruct subject on injection technique, dosing regimen, and use of eDiary.
 - Schedule next visit.

8.9.3.3 *Month 12 Visit*

The following procedures will be performed by the investigator or delegate:

- Record social and physical activity.
- Physical examination.
- Vital signs.
- Body weight and height (height optional for subjects ≥ 18 years).
- Obtain blood sample for biochemistry and hematology assessments.
- Obtain blood samples for:
 - Inhibitors against FIX.
 - Antibodies against rIX-FP.
 - Antibodies against CHO cell-derived proteins.
- Obtain blood sample for measurement of plasma FIX activity (central and local laboratory).
- Review subject eDiary.
- Assess treatment efficacy for major bleeding episodes, if applicable.
- Review treatment regimen (ie, dose and / or treatment interval) and modify, if necessary. Record any changes in treatment regimen in the eCRF.

- Record AEs and concomitant therapies.
- Parents or the caregiver of subjects to complete Hemo-Sat questionnaire (for subjects who transferred from the CSL654_3002 lead-in study).

- If considered necessary, reinstruct subject on injection technique, dosing regimen, and use of eDiary.
- Schedule next visit.

8.9.3.4 Months 18, 30, 42, and 54 Visits

The following procedures will be performed by the investigator or delegate:

- Record social and physical activity.
- Body weight.
- Obtain blood samples for inhibitors against FIX.
- Obtain blood sample for measurement of plasma FIX activity (central laboratory).
- Review subject eDiary.
- Assess treatment efficacy for major bleeding episodes, if applicable.
- Review treatment regimen (ie, dose and treatment interval) and modify, if necessary. Record any changes in treatment regimen in the eCRF.
- Record AEs and concomitant therapies.
- If considered necessary, reinstruct subject on injection technique, dosing regimen, and use of eDiary.
- Schedule next visit.

8.9.3.5 *Months 24, 36, 48, and 60 Visits*

The following procedures will be performed by the investigator or delegate:

- Record social and physical activity.
- Physical examination.
- Vital signs.
- Body weight and height.
- Obtain blood samples for:
 - Inhibitors against FIX.
 - Antibodies against rIX-FP.
 - Antibodies against CHO cell-derived proteins
- Obtain blood sample for measurement of plasma FIX activity (central laboratory).
- Review subject eDiary.
- Assess treatment efficacy for major bleeding episodes, if applicable.
- Review treatment regimen (ie, dose and treatment interval) and modify, if necessary.
Record any changes in treatment regimen in the eCRF.
- Record AEs and concomitant therapies.
- If considered necessary, reinstruct subject on injection technique, dosing regimen, and use of eDiary.
- Schedule next study visit.

8.9.4 **Other Visits During the Treatment Period (Arm 4 only)**

8.9.4.1 *First 10 to 20 administrations of rIX-FP*

Subjects must be treated in a clinic/hospital setting capable of treating severe allergic reactions during the initial 10 (required minimum) to 20 (at investigator's discretion) infusions. The first two doses must be monitored under medical supervision for at least 3 hours, and the remaining doses are monitored for at least 30 minutes. Some of those visits for administrations of rIX-FP can occur during the scheduled monthly visits after samples for laboratory testing are

collected. The dose, administration information, reason for the dose and assessment of local tolerability must be recorded in the eCRF.

8.9.4.2 Visit at Month 1, 2, 3, 4, 5, 6, 7, 8, 9, 10, 11 and 12

Subjects will visit the study center as outlined in the Schedule of Assessments ([Table D](#)), preferably within 2 days prior to the next planned infusion of rIX-FP (or as close to the next rIX-FP infusion as possible) if subject is receiving routine prophylaxis.

The following procedures will be performed at every visit:

- Physical examination.
- Vital signs.
- Weight and height.
- Review concomitant therapy.
- Review AEs since last visit.
- Review the subject eDiary (if applicable) and investigator assessment of efficacy for treated bleeding events.
- If considered necessary, reinstruct subject/caregiver on injection technique, dosing regimen, and use of eDiary.

The following procedures will be performed, in addition to the procedures listed above:

- Blood samples for FIX inhibitors at Months 1, 2, 3, 4, 5, 6, 9 and 12 (CL). In addition, inhibitor testing should be performed at any time if there is any suspicion of inhibitor development.
- Blood samples for antibodies against rIX-FP and CHO cells at Months 6 and 12 (CL).
- Blood samples for local laboratory safety evaluation (hematology and Biochemistry) at Month 12 visit.
- Blood samples for FIX activity level at Months 1, 2, 3, 6 and 12 (CL).

If a subject receives less than 3 doses per month, they may omit the site visit(s) until the first 5 doses have been administered.

In the event a subject misses a study visit, the study personnel should contact the study subject by telephone and collect pertinent study-related information and document accordingly in the medical record. All subject data should be reviewed at the next scheduled visit and recorded in the CRF.

In the event a subject misses any visit at which testing for inhibitor is required, an unscheduled visit should be arranged as soon as possible during the subject's first 20 EDs, otherwise all required laboratory tests can be conducted during the next site visit.

The subject's caregiver may begin administering rIX-FP at home after the subject has received a minimum of 10 treatments of rIX-FP at the site. The investigator or delegate will ensure that the caregiver has been trained sufficiently to allow for home therapy to occur in the subsequent months of the study. The study center personnel will instruct the caregiver on the reconstitution and administration of rIX-FP and correct completion of the eDiary prior to issuing the eDiary as outlined in [Section 8.2](#).

8.9.4.3 Months 15, 18, 21, 24, 27, 30 and 33 Visits

Subjects will visit the study center as outlined in the Schedule of Assessments ([Table D](#)), preferably within 24 hours (or as close to the next rIX-FP infusion as possible) prior to the next planned infusion of rIX-FP.

The following procedures will be performed by the investigator or delegate at every visit:

- Physical examination.
- Vital signs.
- Weight and height.
- Review concomitant therapy.
- Review AEs.
- Review the subject eDiary (if applicable) and investigator assessment of efficacy.
- If considered necessary, reinstruct caregiver/subject on injection technique, dosing regimen, and use of eDiary.

The following procedures will be performed, in addition to the procedures listed above at Month 18, 24 and 30 Visit ONLY:

- Obtain blood samples for inhibitor to FIX (CL).

The following procedures will be performed, in addition to the procedures listed above at Month 24 Visit ONLY:

- Obtain blood sample for biochemistry and hematology assessments (LL).
- Blood samples for FIX activity and antibodies against rIX-FP and CHO cells (CL).

8.9.5 Completion of 50 rIX-FP EDs During the Study (all subjects)

The following procedures will be performed by the investigator or delegate:

- Obtain central laboratory blood samples for:
 - Inhibitors against FIX.
 - Antibodies against rIX-FP
 - Antibodies against CHO cell-derived proteins.
- Record AEs and concomitant therapies.

8.9.6 Unscheduled Visits if Inhibitor to FIX is confirmed

The following procedures will be performed:

- Obtain blood sample for genotyping if no test results are available in subject medical records.
- Obtain blood samples for PK assessment if feasible.
- Review concomitant therapy.
- Review AEs.
- Review the eDiary (if applicable) and investigator assessment of efficacy of any treated bleeding episodes.

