4.2 SUBJECT WITHDRAWAL

4.2.1 Subject Withdrawal

Subjects may withdraw from the study at any time at their own request, or they may be withdrawn at any time at the discretion of the investigator or CSL for safety, behavioral or administrative reasons (eg, due to an AE, protocol violation, loss to follow-up, subject noncompliance, and study termination).

In accordance with the International Conference on Harmonisation (ICH) principles of Good Clinical Practice (GCP) the investigator always has the option to advise a subject to withdraw from the study if the subject's safety or well-being is compromised by his further participation in the study. Concern for the interests of the subject must always prevail over the interests of the study.

Subjects may be discontinued from receiving the study product and participating in any further study procedures if:

- Subjects in France may be discontinued from receiving the study product and participating in any further study procedures if the subject is confirmed to have

developed an inhibitor against FIX with a titer > 5 BU/mL. Alternatively, at the investigator's discretion, a subject who develops inhibitors to rIX-FP may remain in the study until a better treatment option becomes available to the subject or until the end of study visit, whichever comes first.

- The subject uses a marketed FIX during the study, except when rIX-FP is not available and / or if a marketed FIX is required as rescue medication.
- The subject does not comply with the assigned treatment schedule or is, in the opinion of the investigator and / or CSL, delinquent or delayed in using the eDiary.
- **For subjects in Arm 3 only (not applicable to France:** if a major non-emergency surgical procedure is not performed within approximately 8 weeks of starting the rIX-FP (100 IU/kg) PK evaluation period, CSL may request the subject to be rescreened or withdrawn from the study.
- **For subjects in Arm 4 only:** if a major surgery (except permanent venous access placement or removal, circumcision and some non-complicated unavoidable dental procedures) is required during the study or severe hypersensitivity or inhibitor to FIX (titer > 5 BU/mL) occurred, the subject should be withdrawn from the study.

If a subject is withdrawn from the study or further participation is declined, they will continue to have access to medical care and will be treated as per routine medical practice.

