8.6 INHIBITORS AND ANTIBODIES

The presence of antibodies against rIX-FP and CHO cells and inhibitors of FIX will be assessed by the central laboratory. Details regarding sample collection, handling, deep freezing of samples and shipment to the central laboratory are given in the Laboratory Manual in the Investigator Site File.

A tiered approach for immunogenicity testing for antibodies to rIX-FP will be employed during the study:

1. **Screening assay:** The screening assay is a direct-binding ELISA assay, capable of detecting antibodies against rIX-FP in blood samples from subjects.
2. **Confirmation assays:** If the antibody titer is above the cut-off level for the screening assay, the same sample will be tested in a separate direct-binding ELISA assay to confirm the specific antibody signal and to discriminate between plasma-derived FIX, rIX-FP, and albumin antibodies. In the event that all confirmation assays are negative, the screening assay will be considered a false positive result.
3. **Neutralization assay for inhibitors:** The neutralizing capacity of antibodies will be assessed by a FIX potency assay. To quantify anti-FIX neutralizing antibodies, the Bethesda assay with the Nijmegen modification will be used, and the results expressed as Bethesda Units per mL (BU/mL).

In cases where the inhibitor titer is determined to be above the cut-off level (0.6 BU/mL), a second blood sample should be collected and be tested by the central laboratory for confirmation, and additional testing such as PK / incremental recovery tests will be performed. The subject's information will be presented to the SMT and IDMC for its recommendation.

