11.3.3.1 Primary Safety Analysis

The number and proportion of subjects with positive tests for inhibitors to FIX during the study will be tabulated. Subjects must have two tests that are positive to be classified as having an

inhibitor. Inhibitor antibodies against FIX will be categorized as low titer (≥ 0.6 to 5 BU/mL) and high titer (> 5 BU/mL). A two-sided 95% exact Clopper-Pearson binomial confidence interval (one-sided if no events are observed) for inhibitor development among subjects treated with rIX-FP, by PTP and PUP, will be presented.

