11.3.3.7 Inhibitors to Factor IX

The number and proportion of subjects with a confirmed FIX inhibitor titer above the cut-off level (≥ 0.6 BU/mL) will be tabulated.

11.3.3.8 *Antibodies to rIX-FP and CHO Cell-derived Proteins*

The number and percentage of subjects with rIX-FP and CHO cell-derived protein antibody titers above the cut-off level for the respective confirmation assays will be tabulated.

11.3.3.9 *Additional Safety Information from the Surgery and Subcutaneous Substudies*

Safety assessments and events, including AEs, which occur during the protocol-defined preoperative, intraoperative, or postoperative periods of the surgery substudy and in the SC substudy will be summarized in separate tables.

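### The retest trigger in 8.6 does not match the ≥ 0.6 BU/mL case definition, and no titer is scheduled after confirmation, so the low/high titer category in Arm 4 can err downward

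*Protocol*

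**What the plan says.** **Trigger for the second sample.** Protocol 8.6: "In cases where the inhibitor titer is determined to be above the cut-off level (0.6 BU/mL), a second blood sample should be collected".

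**Case definition.** Protocol 11.3.3.1: "Subjects must have two tests that are positive to be classified as having an" inhibitor. The lower bound is ≥ 0.6 BU/mL in protocol 3.6.1 (the IDMC trigger), 11.3.3.1 and 11.3.3.7. SAP 4.13.2 also uses ≥ 0.6, confirmed by retesting, with both tests at a central laboratory. Protocol 11.3.3.7 reads: "The number and proportion of subjects with a confirmed FIX inhibitor titer above the cut-off level (≥ 0.6 BU/mL) will be tabulated".

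**Titer category.** Protocol 11.3.3.1: "Inhibitor antibodies against FIX will be categorized as low titer" (0.6 to 5 BU/mL) or high titer (over 5). It does not say whether the first, the confirmatory or the highest titer sets the category. SAP 4.13.2 has no low/high split, and SAP section 8 does not list dropping it as a deviation.

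**Visit after confirmation.** Protocol 8.9.6 lists genotyping where no result exists, "Obtain blood samples for PK assessment if feasible", concomitant therapy, adverse events, and the eDiary with the efficacy assessment. No inhibitor titer is listed.

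**Rule that uses the titer.** Protocol 4.2.1, for Arm 4: if "inhibitor to FIX (titer > 5 BU/mL) occurred, the subject should be withdrawn from the study".

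**Scheduled inhibitor samples, Arm 4.** Months 1 to 6, 9 and 12 (8.9.4.2); then, from 8.9.4.3, "in addition to the procedures listed above at Month 18, 24 and 30 Visit ONLY"; also at 50 exposure days (EDs) (8.9.5) and at end of study (8.9.7), which Table D places at Month 36.

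**The concern.** Inhibitor development is the primary safety endpoint, and the previously untreated arm (PUPs) may have as few as 13 subjects, so each subject weighs heavily. Two things look wrong.

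First, the instruction that produces the second test is worded more narrowly than the definition that needs it. A first result exactly on the boundary qualifies as a positive but does not prompt the sample that would confirm it.

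Second, the protocol promises a low/high split and has an Arm 4 criterion that turns on 5 BU/mL, yet the visit created for confirmed cases does not collect the measurement that both depend on. A titer may keep rising after confirmation. If the later value is not measured, the subject stays in the low-titer group. Fewer measurements can only lower the highest titer observed, so this error runs in one direction.

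**Working it through.** The plan states no event count, precision target or power for this endpoint, so there is no figure to reproduce. The check sets the texts side by side and then sizes one affected subject.

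**1. A first result of exactly 0.6 BU/mL**
- 8.6, read literally: 0.6 is not above 0.6, so no second sample is called for.
- 11.3.3.1 and SAP 4.13.2: 0.6 meets ≥ 0.6, so it is a positive that needs a second one.
- 11.3.3.7 uses the same phrase as 8.6 but glosses it as ≥ 0.6, so the intended trigger is very probably ≥ 0.6.
- 11.3.3.1 asks for two positive tests and does not say they must be consecutive. A later scheduled positive could therefore supply the second.

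The documents do not give the reporting precision of the assay. If results are reported to one decimal (an assumption), exactly 0.6 is an ordinary reportable value.

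**2. Time to the next scheduled titer in Arm 4**
- Months 1 to 6: 1 month between samples.
- Months 6 to 9 and 9 to 12: 3 months.
- Months 12 to 18, 18 to 24, 24 to 30 and 30 to 36: 6 months, which is 6 × 28 days = 24 weeks with the 28-day month of Table A (defined there for Arms 1 to 3), or about 26 calendar weeks.
- The 50-ED sample adds one point. On weekly dosing from Day 1 it falls at 50 weeks: 50/4 = 12.5 months of 28 days, or 350/30.4375 = 11.5 calendar months. For such a subject it lies close to Month 12 and barely shortens the later gaps.

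**3. Effect on the primary count**
A subject reaches the 8.9.6 visit only after confirmation, so he already has two positive tests and is in the numerator. A later rise changes nothing there. Effect of the missing titer on the count and its interval: zero.

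**4. Size of one affected subject, assuming all 13 PUPs are evaluable**
- Proportion: 1/13 = 7.7%.
- Exact Clopper-Pearson 95% interval for 1/13: 0.2% to 36.0%.
- If that case were lost: 0/13, with one-sided 95% upper limit 1 − 0.05^(1/13) = 20.6% (11.3.3.1 prescribes one-sided limits for zero events); the two-sided upper limit is 24.7%.
- Under SAP 4.13.2, a PUP with fewer than 50 EDs enters the denominator only if confirmed. Losing such a case gives 0/12, with one-sided limit 1 − 0.05^(1/12) = 22.1%.
- One subject placed in low instead of high titer: the high-titer proportion moves by 1/13 = 7.7 percentage points, and total incidence does not move.

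**The case against.** Three stronger readings are tempting, and the documents do not support them.

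- *High-titer cases are missed in the primary analysis.* They are not. The primary endpoint counts subjects with an inhibitor of any titer, and a subject at the 8.9.6 visit is already counted.
- *A result of exactly 0.6 can never become a case.* Too strong. 11.3.3.7 shows that ≥ is meant, and 11.3.3.1 leaves room for a later positive.
- *The 5 BU/mL criterion cannot act until the next calendar sample, while some 24 to 26 weekly doses go by.* Also too strong. Protocol 7.1 requires contact with the medical monitor before any further dose once an inhibitor develops. Section 8.6 says PK or recovery tests will be performed and sends the case to the Safety Management Team and the IDMC; 3.6.1 and 3.6.2.1 provide for ad hoc meetings after each newly confirmed Arm 4 inhibitor. Adverse events associated with a confirmed inhibitor are reported as serious and followed up (9.1.2, 9.5.1, 9.6.1). Unscheduled visits are allowed at any time (8.9.10), and end-of-study sampling is attempted at withdrawal (4.2.2, 8.9.7).

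These safeguards make it likely that many titers would be repeated in practice. What they do not do is require one. The instruction to test on any suspicion sits in the section for Months 1 to 12 (8.9.4.2) and concerns detection; extra tests under 10.3 are discretionary.

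It can also be said that the SAP omits the low/high split and takes precedence where methods differ, so nothing in the analysis depends on it. That is fair as far as it goes. But the protocol places the split in its primary safety analysis, and the SAP does not declare it dropped, so the two documents still need to agree. Finally, 11.3.3.1 does not prevent a later scheduled result above 5 BU/mL from setting the category. The downward error is possible rather than certain.

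**Conclusion.** The point holds in two limited parts.

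1. The trigger in 8.6 and the case definition disagree at exactly 0.6 BU/mL. The intent is clear, so this is a wording correction, but it touches the primary count: a case lost this way in 13 PUPs would turn 1/13 (7.7%, 0.2% to 36.0%) into 0/13 (one-sided upper limit 20.6%).
2. No titer is required after confirmation, and the titer that sets the category is undefined. In Arm 4 after Month 12 the scheduled gap is up to about 6 months, so a rise above 5 BU/mL can be seen late or missed. The high-titer count can err only downward, by 7.7 percentage points per subject. The count of subjects with inhibitors and its interval are not affected.

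The percentages assume all 13 PUPs are evaluable; the SAP denominator may be smaller. The 6 months is the worst case, with confirmation just after a scheduled sample from Month 12 onward and no discretionary testing. New sampling matters only for Arm 4, because participation of previously treated patients is closed (protocol revision history, Amendment 6) and their data have been reported (SAP 3.1).

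**What to change.** - **8.6:** change the trigger to *at or above 0.6 BU/mL*.
- **8.9.6:** add a central-laboratory FIX inhibitor titer for Arm 4.
- **11.3.3.1 and SAP 4.13.2:** classify low versus high on the highest central-laboratory titer in confirmed cases, and put the split into SAP 4.13.2.
- **Data check before lock:** list any first central result of exactly 0.6 BU/mL that had no second sample.
- **4.2.1 and 8.9.6:** reconcile the passages that turn on 5 BU/mL with the procedures that would supply the titer. No withdrawal or treatment rule is proposed here.

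The wording, the classification rule and the data check need no extra blood. The added titer costs one small tube in the few Arm 4 subjects with a confirmed inhibitor. It cannot always share an existing draw, because both draws in 8.9.6 are conditional and these are paediatric subjects. The high-titer count may come out less favourable. No sample size or error rate changes.
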